All 50 participants receiving AZD7442 exhibited > 4-fold increases in neutralizing antibody titer at 7 days after treatment; all 40 patients with available data at 30 days after treatment maintained this increase out to Day 211. Participants in the 300-mg cohorts further maintained this 4-fold increase in nAb titre out to Day 271 post-treatment. These results are consistent with the expected pharmacodynamic activity of AZD7442 and demonstrate a dose dependent increase in nAb, with the 3000 mg dose cohorts showing approximately 3.5, 16.1, and 29.7 greater fold changes than the 1000 mg, 300 mg IV, and 300 mg IM, respectively, after 7 days of treatment; 2.7, 9.0, and 13.0 greater fold changes after 150 days of treatment; and 4.3, 10.4, and 13.7 greater fold changes after 210 days of treatment. Across all doses and timepoints evaluated, the levels of nAbs exceeded the mean nAb titres measured in the same assay in 28 individual convalescent plasma samples.

Specifically, participants treated with 300 mg of AZD7442, either IM or IV, exhibit approximately 10 to 15-fold higher GMT at Day 91, 6 to 8-fold higher GMT at Day 151, and 2 to 3-fold higher GMT at Day 271 compared to the GMT measured in convalescent plasma from SARS-COV-2 patients (GMT = 50; n = 28). No safety signals were observed in this healthy adult population. These results demonstrated an acceptable safety profile for AZD7442, including no observed infusion-related reactions, injection site reactions, or hypersensitivity reactions. Overall, the results support the use of AZD7442 in further clinical studies.

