11.7 Accountability procedures

Local pharmacy personnel will be responsible for ensuring that the IMP is managed and dispensed to participants in accordance with the duly approved current protocol.

Accountability logs for AZD8895 and AZD1061 are included in the Pharmacy Pack provided by CTR upon site activation.

Trial specific accountability is not required for vaccines.

The investigator is responsible for keeping accurate records of the clinical supplies received from AstraZeneca or designee, of the amount dispensed to and returned by the participants and the amount remaining at the conclusion of the trial.

Upon completion or termination of the trial, all unused and/or partially used investigational product will be destroyed at the site per institutional policy after authorisation from CTR. It is the Investigator's responsibility to arrange for disposal of all empty containers, provided that procedures for proper disposal have been established according to applicable federal, state, local and institutional guidelines and procedures, and provided that appropriate records of disposal are kept.

12 Sample Management

Sites will be provided with a translational sample collection kit. Up to 50ml of blood will be collected from participants at the following timepoints:

- Baseline (Predose)
- 28, 56, 112 and 180 days post AZD7442

Samples will be processed and frozen onsite. The CTR will arrange regular batch collections of samples on dry ice to the relevant Laboratory. Samples may be stored by laboratories approved by the Sponsor.

A subset of sites will be asked to provide fresh samples for additional analysis. Full details on sample collection and management can be found in the Laboratory Manual.

Lateral flow tests for SARS-CoV-2 infection will be performed for a subset of participants routinely on day 0, 28, 56, 112 and 180. If the lateral flow test is positive for SARS-CoV-2 infection, a nasal PCR swab will be taken to be sent for testing.

All participants testing positive to SARS-CoV-2 throughout the trial will also be asked to send a nasal PCR swab for testing.

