13.1 Assessments

Baseline Assessments

All baseline assessments should be performed after consent has been obtained and within 28 days of treatment. Participants will be required to attend clinic for blood sample collection and treatment. The following assessments will need to be done:

- Completion of eligibility checklist form
- Participant informed consent
- Full Medical History
- Randomisation as per Section 9.5 of the protocol
- Participants should be asked about their previous SARS-CoV-2 vaccination history. The information should be collected on the SARS-CoV-2 vaccine form.
- Prior and Concomitant Medications Review of any medications received within 28 days before the first dose of trial treatment
- Participant behavioural questionnaires (risk behaviour changes, PROMIS 10, EQ-5D-5L)

AZD7442 treatment (this can be done on the same day as baseline assessments)

Day 0

- A negative urine dipstick pregnancy test should be performed to confirm eligibility for women of child-bearing potential.
- Toxicity assessment (CTCAE 5.0)
- Blood sample collection and completion of the sample eCRF
- Safety bloods (full blood count (FBC), Urea and electrolytes (U&E), Liver function test (LFT) and bone profile)
- Full Physical Examination including vital signs, weight and height
- Blood sample collection prior to AZD7442 dosing and completion of the sample eCRF
- Routine (asymptomatic) lateral flow testing for SARS-CoV-2 infection (only subset of participants). If the lateral flow test is positive for SARS-CoV-2 infection, a nasal PCR swab should be taken to be sent for testing.

NB: The assessments above should be performed *before* the administration of AZD7442.

• Dosing with AZD7442

On Day 14 post AZD7442 (+/- 3 days):

• Toxicity assessment via telephone consultation with patient to check on symptoms.

On Day 28 post AZD7442 (+/- 3 days):

- Clinical review
- Vital signs
- Blood sample collection and completion of the sample eCRF
- Safety blood samples (FBC, U&E, LFT and bone profile)
- Concomitant Medications Review
- Toxicity assessment (CTCAE 5.0)
- Routine (asymptomatic) lateral flow testing for SARS-CoV-2 infection (only subset of participants). If the lateral flow test is positive for SARS-CoV-2 infection, a nasal PCR swab should be taken to be sent for testing.

NB: The assessments above should be performed *before* the administration of SARS-CoV-2 vaccine booster.

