13.1.1 Reduction of follow up period

The Food and Drug Administration (FDA) released an announcement at the end of January 2023 advising that the use of Evusheld should be limited to when the combined frequency of non-susceptible SARS-CoV-2 variants nationally is less than or equal to 90 %. The non-susceptible SARS-CoV-2 variants included the XBB, CH.1.1 and BQ.1 sub-lineages of the Omicron variant. At this time in the U.S., fewer than 10 % of circulating variants were susceptible to Evusheld, so the FDA removed the use of Evusheld until further notice in the U.S. The link below provides further information regarding this announcement: https://www.fda.gov/drugs/drug-safety-and-availability/fda-announces-evusheld-not-currently-authorized-emergency-use-us

At this time the UK had not yet reached a threshold where \geq 90 % of the circulating variants were Evusheld-resistant SARS-CoV-2 variants so the decision was made to continue the trial as planned but closely monitor the data published weekly by the Office for National Statistics (ONS).

After monitoring the data on the UK SARS-CoV-2 infection survey that was published by the ONS over the following months, the decision was made to pause recruitment within the RAPID-PROTECTION study at the beginning of April 2023, since the percentage of circulating Evusheld resistant SARS-CoV-2 variants had exceeded the 90 % threshold. The decision was also made to reduce the follow-up period from 12 months to 6 months for all patients.

A Changes to Follow up Notification form has been created to notify existing participants of these changes and this should be provided to all participants as soon as possible.

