16.1 Main analysis

16.1.1 Immunogenicity at 28 days following administration of AZD7442

The function and magnitude of SARS-CoV-2 specific antibody and T cell responses will be measured at baseline and at additional multiple timepoints after the administration of AZD7442. The immunological effect of the study interventions will be determined by comparison of the results of immunological assessments at baseline and subsequent time points.

Assays will quantify the amount of serum antibodies to the spike (S) and the nucleocapsid (N) antigens of SARS-CoV-2. This assay will enable the discrimination of antibody responses to SARS-CoV-2 that results from vaccination and/or SARS-CoV-2 infection. Ab function, including viral neutralisation will be assessed.

The magnitude and function of SARS-CoV-2 specific T cell responses following the booster vaccination will use assays that give insight into T cell function. Laboratories will measure neutralizing antibodies to SARS-CoV-2 using validated wild-type neutralization assay or pseudo-neutralization assays.

Comparisons of immunogenicity outcomes will be made with age and gender matched healthy controls from the PROVENT III trial. Group data will be requested from the PROVENT trial. Values will be log-transformed and mean and standard deviation calculated for the same groups at each timepoint. The PROVENT data will be used to calculate the overall standard deviation of a population with the same age / sex distribution as each of our cohorts at each timepoint. The mean and standard

deviation and its 95% confidence interval will be calculated for each cohort for comparison with the PROVENT data at each timepoint.

The ratio of the variances in the log transformed domain will be tested to assess if it is significantly different from 1. All tests will be one sided and focussed on if the trial patients perform less well than the healthy volunteers in terms of response to vaccine. Results will be reported as the ratio of variances, 95% confidence intervals and p values.

16.1.2 Immunogenicity at 28 days following administration of AZD7442 followed by a SARS-CoV-2 vaccine 28 days later (outcome measured at day 56)

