To assess if treatment with AZD7442 followed by a SARS-CoV-2 vaccine 28 days later will increase levels of anti-SARS-COVID-2-anti S-RBD neutralising antibodies in patients. This will be assessed in a hierarchical way firstly comparing age-matched healthy controls from the PROVENT III trial of the AZD7442 and AZD1222 all patients (groups 1, 2, 3 and 4) on both point estimator and variance and if the variance is greater than subdividing into the individual groups by patient group.

Comparisons will be made between each of the vaccines using an ANCOVA model with baseline value as a covariate. An exploratory analysis will be conducted to examine differences between the vaccine types and patient cohorts (see section 16.3 below).

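### The immunogenicity baseline precedes AZD7442, so a rise to Day 56 in anti-spike or neutralising antibody cannot isolate the booster effect; the pre-booster Day 28 value should be its reference and covariate

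*Protocol*

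**What the plan says.** Section 16.1.1 says the immunological effect of the study interventions is "determined by comparison of the results of immunological assessments at baseline and subsequent time points". Its one-sided tests against healthy volunteers are "focussed on if the trial patients perform less well than the healthy volunteers in terms of response to vaccine", although the section is headed as immunogenicity 28 days after AZD7442.

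Section 16.1.2 covers AZD7442 followed by the booster, with "outcome measured at day 56". For the randomised comparison it says: "Comparisons will be made between each of the vaccines using an ANCOVA model with baseline value as a covariate". It does not say which sample supplies that value.

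The rest of the protocol does. Section 12 lists the baseline sample as the pre-dose one and Day 28 as a separate, later time point. Section 13.1 schedules at Day 0: "Blood sample collection prior to AZD7442 dosing and completion of the sample eCRF". Table 6 marks the Day 0 sample as collected before AZD7442. Sections 11.1 and 13.1 place the booster after the Day 28 bloods. Nowhere in Section 16 is Day 28 named as the reference or covariate for the booster.

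**The concern.** AZD7442 is given between the baseline sample and the booster. By Section 4.4 it binds the receptor-binding domain of the spike protein, which is also the target of the neutralising anti-S-RBD readout in Section 16.1.2. Of the Phase I study, Section 4.6 reports: "All 50 participants receiving AZD7442 exhibited > 4-fold increases in neutralizing antibody titer at 7 days after treatment". It also puts the half-life at about 90 days, so most of the drug remains at Day 56. A rise from baseline is then expected in everyone, whatever the participant's own response. The S and N assays are said to separate vaccination from infection; they are not said to separate infused from vaccine-induced antibody.

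The protocol does ask about the booster's own contribution. Sections 3.2 and 4.6.4 ask whether vaccination further enhances protection, and the co-primary immune objective in Table 1 concerns the response when a vaccine follows AZD7442 by 28 days. Section 6 also allows cohorts to be expanded or closed according to immunogenicity. If that were judged on anti-spike or neutralising antibody, infused drug could influence the decision.

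**Working it through.** **The plan's own figures.** Section 15.3 gives a difference of 0.5 (log domain), SD 1, 90% power and 5% significance. One-sided, n = 2(1.645 + 1.282)² × 1² / 0.5² = 68.5, so 69 per group (70 with the t distribution). Then 4 × 70 = 280, and 280 / 0.80 = 350. These reproduce, but they size the comparison with PROVENT. The protocol gives no sample size for the booster ANCOVA.

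**What a ratio to baseline contains.** Set own anti-spike antibody to 1 at Day 0, and let k be the ratio of infused to own antibody at Day 28. The protocol does not give k; values of 1 to 30 are assumed. From the 90-day half-life, the fraction of drug left 28 days later is 0.5^(28/90) = 0.806. With no booster response:

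- Day 28 total = 1 + k
- Day 56 total = 1 + 0.806k

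| k | Day 56 / Day 0 | Day 56 / Day 28 |
|---|---|---|
| 1 | 1.81 | 0.90 |
| 4 | 4.22 | 0.84 |
| 10 | 9.06 | 0.82 |
| 30 | 25.18 | 0.81 |

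The true booster effect in every row is a ratio of 1. The ratio to Day 0 is far above it. The ratio to Day 28 falls below it by at most 1 − 0.806 = 0.194, about 19%, through decay of the drug.

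**What remains masked.** At k = 10, suppose one booster doubles own antibody and the other raises it fourfold. The observed ratio of arms at Day 56 is (4 + 8.06) / (2 + 8.06) = 12.06 / 10.06 = 1.20, against a true ratio of 2. This comes from the infused antibody in the Day 56 outcome and is the same under either covariate.

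**The ANCOVA covariate.** Total anti-spike antibody was simulated for 280 participants, 140 per arm, with a twofold boost in the reference arm. Assumed log-scale SDs were own antibody 1.0, infused 0.4, boost 0.5 and assay 0.15. The test was two-sided at 5%.

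- Type I error over k = 1 to 30 was 4.6–4.9% with the Day 0 covariate and 4.7–5.6% with Day 28.
- For a 1.5-fold booster difference, the mean estimated effects under the two covariates agreed within 0.001.
- Power for that difference:

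| k | Day 0 covariate | Day 28 covariate |
|---|---|---|
| 1 | 100% | 100% |
| 4 | 95% | 97% |
| 10 | 68% | 85% |
| 30 | 20% | 45% |

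At k = 1 the SDs of the estimate were also nearly equal (0.053 and 0.055), so the equal power there does not merely hide a gain behind the 100% ceiling.

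**The case against.** The strongest defence is that a Day 0 reference fits part of the stated aim. Section 16.1.2 and hypothesis 3 in Section 4.7.1 speak of AZD7442 together with a vaccine, and for that combined regimen a pre-AZD7442 reference is coherent. This stands, and Day 0 should be kept for that purpose. It does not answer the question of what the booster adds.

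A reader might infer that the randomised comparison is biased. It is not: both arms receive AZD7442 before the booster, so a pre-treatment covariate is legitimate and only precision is at issue. Comparing the vaccines is also a secondary objective.

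A reader might infer that infused drug alone would meet the co-primary objective. The documents do not support this. No success rule based on a rise from baseline is stated, and the formal tests in Sections 16.1.1 and 16.1.2 compare patients with PROVENT controls, not with their own Day 0 values.

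An SAP might define baseline for this model. Section 15.1 places randomisation at Day 28, which would make Day 28 a natural baseline; Sections 9.5 and 13.1 place it at enrolment or baseline. The text is therefore open on this point, but the protocol's own usage for blood samples is pre-dose, and Section 16.1.1 fixes baseline as the general reference.

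Part of the remedy is already planned. Table 1, in the row on vaccine effect on antibody titres, quantifies AZD7442 at Days 0, 28, 56, 112 and 180, and Section 12.1 lists T-cell assays. Section 16, however, does not use the drug level to interpret the antibody readouts.

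**Conclusion.** The point holds for anti-spike and neutralising antibody. By the protocol's usage, change from baseline to Day 56 mixes infused antibody with booster response and cannot isolate the latter. T-cell and anti-nucleocapsid readouts are not directly affected.

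For the ANCOVA the issue is efficiency. Its size rests on the assumed ratio of infused to own antibody and the assumed SDs: no power gain from Day 28 at a ratio of 1, and 68% against 85% at 10. No general sample-size saving can be claimed from this.

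Two further inferences go too far. Section 13.1.1 says: "The non-susceptible SARS-CoV-2 variants included the XBB, CH.1.1 and BQ.1 sub-lineages of the Omicron variant". That passage explains the recruitment pause and the shorter follow-up. Section 12.1 plans neutralisation against variants but names none, so an assay free of AZD7442 activity is not shown to be planned. Nor does Section 15.1 name cohort as a randomisation stratum, although Section 6 speaks of patients stratified by cohort. A cohort term in the model is for precision; its absence is not a demonstrated mismatch with the randomisation.

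**What to change.** - In Section 16.1.2, name the pre-booster Day 28 value as the reference for booster-specific response and as the ANCOVA covariate: log Day 56 on arm, log Day 28 and cohort. Keep Day 0 as the reference for the combined-regimen aim.
- Interpret Day 28 to Day 56 change in anti-spike and neutralising antibody beside the AZD7442 concentration at both days, because decay alone can lower it by up to about 19% and residual drug still masks the booster. Report the planned T-cell readouts alongside. Confirm that Day 56 drug levels are obtained: the titre row of Table 1 includes that day, but its pharmacokinetics row does not.
- In Section 16.1.1, describe the Day 28 analysis as response after AZD7442, since the booster follows those bloods.
- Reconcile the timing of randomisation between Section 15.1 and Sections 9.5 and 13.1. The Day 28 value precedes the booster either way, but is strictly pre-randomisation only under Section 15.1.

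The cost is wording in the protocol and any SAP. The Day 28 sample is already scheduled for everyone, and Section 10.2 makes it part of the minimum sought from participants who miss visits. The limit is that this does not fully separate infused from vaccine-induced antibody.

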16.1.3 Analysis of SARS-CoV-2 infection

Incidence of SARS-CoV-2 infection will be a descriptive analysis and summarised by incidence rates and 95% confidence intervals. Comparison of incidence rates between groups will be performed using Poisson regression and summarised as Incidence rate ratios, risk differences, 95% confidence intervals and p values.

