ISF	Investigator Site File
ISRCTN	International Standard Randomised Controlled Trial Number
IU	International Unit
LFT	Liver function test
МА	Marketing Authorisation
MedDRA	Medical Dictionary for Regulatory Activities
MHRA	Medicine and Healthcare products Regulatory Agency
NHS	National Health Service
NIMP	Non-Investigational Medicinal Product
NIV	Non-invasive Ventilation

ovc	Oxford Vaccine Centre
PCR	Polymerase Chain Reaction
PI	Principal Investigator
PIS	Participant Information Sheet
QA	Quality Assurance
QC	Quality control
QP	Qualified Person
R&D	Research and Development
RCT	Randomised Controlled Trial
REC	Research Ethics Committee
SAE	Serious Adverse Event
SAR	Serious Adverse Reaction
SmPC	Summary Product Characteristics
SOP	Standard Operating Procedure
SUSAR	Suspected Unexpected Serious Adverse Reactions
TMF	Trial Master File
ТМG	Trial Management Group
TSC	Trial Steering Committee
U&E	Urea and electrolytes
WHO	World Health Organisation
w/v	Weight per volume

1. Amendment History

The following amendments and/or administrative changes have been made to this protocol since the implementation of the first approved version.

Amendment No.	Protocol version no.	Date issued	Summary of changes made since previous version
n/a	1.1	26/05/2022	Minor amendments to include correction of typographical and formatting errors, minor clarification to some of the inclusion and exclusion criteria, and a minor update to the procedure for nasal PCR swabs for SAR-CoV-2.
n/a	1.2	11/07/2022	Removal of use of vaccine booster lists for identifying eligible participants. Time between study vaccine booster and repeat vaccination with any SARS-CoV2 vaccinations used within the study decreased from 6 months to 3 months.
1	2.0	15/08/2022	Removal of AZ vaccine arm. Increase dose of Evusheld from 300 to 600mg.
2	3.0	14/09/2022	Replacement of Comirnaty and Spikevax vaccines with their respective bivalent versions (Comirnaty bivalent (Original/Omicron BA.1) and Spikevax bivalent (Original/Omicron)).Removal of exclusion criteria no longer applicable.Clarification of vaccine booster supply.Reference to patients who may be referred from their GP/secondary care site.
3	3.1	19/12/2022	Lateral flow tests for all routine asymptomatic SARS-CoV-2 tests for subset of participants at Oxford (PCR swabs will only be taken from patients who test positive for SARS-CoV-2 infection).

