	To assess the effect of a SARS-CoV-2 vaccine on AZD744 monoclonal antibody titres.	Serum samples will be taken at Day 0 (Predose AZD7442), and days 28, 56, 112 and 180 post AZD7442 treatment and vaccination and samples shipped to an AstraZeneca approved laboratory for quantification of the AZD744 monoclonal Abs generated by therapeutic vaccination, natural infection and vaccinations.
Secondary	The incidence of participants who have a post-treatment response (negative/low at baseline to positive at any time post-baseline) for SARS-CoV-2 nucleocapsid antibodies.	Measurement of SARS-CoV-2 anti NP Abs assessed over the course of the study.
	The incidence of SARS-CoV-2 infection in trial participants.	Self-reported throughout the study duration and assessed at follow up visits.
		Lateral flow testing for SARS-CoV-2 infection in a subset of asymptomatic participants on days 0, 28, 56, 112 and 180. If the lateral flow test is positive for SARS-CoV-2, a nasal PCR swab will be taken to be sent for PCR testing.
		Ad-hoc PCR testing in all symptomatic patients.
		Measurement of SARS-CoV-2 Anti-NP IgG titres
	Sequencing of confirmed SARS-CoV-2 infections to identify SARS-CoV-2 variant and potential AZD7442 escape variants.	Lateral flow testing for SARS-CoV-2 infection in a subset of asymptomatic participants on days 0, 28, 56, 112 and 180. If the lateral flow test is positive for SARS- CoV-2, a nasal PCR swab will be taken to be sent for PCR testing.
		Ad-hoc PCR testing in all symptomatic patients.

	To assess the behaviour of the trial participants before and after trial treatment.	Validated behavioural questionnaire completed by the participants at baseline and at multiple time points over the course of the trial.
	To assess if different SARS-CoV-2 vaccines will preferentially enhance humoral and/or T cell responses in immune suppressed patients receiving AZD7442	Assessment of SARS-CoV-2 humoral and cellular responses in patients randomised to receive different SARS-CoV-2 vaccines
	To assess the severity of SARS-CoV-2 infection contracting COVID-19 within the duration of the trial.	Assessment of SARS-CoV-2 severity in participants contracting COVID-19 within the duration of the trial using the WHO Clinical Progression Scale.
Exploratory	To investigate the mechanism of immunogenicity across disorder/disease treatment across the cohorts.	Immune data will be evaluated within and between disease and treatment cohorts.

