12.1 Analysis

Immunogenicity will be assessed by a variety of immunological assays at University of Oxford research laboratories or at designated specialist laboratories. This will include:

- Quantify antibody responses to SARS-CoV-2 Spike and non-Spike antigens
- Assessment of T-cell responses using ex vivo ELISpot assays for interferon gamma and flow cytometry assays or other relevant assays of cellular function and phenotype.
- Assessment of neutralising antibody against live and/or pseudotype SARS-CoV-2 virus variants
- B cell analyses, and Peripheral blood mononuclear cell (PBMC) analysis.

Serology and PK analysis will be conducted at research laboratories as specified in the Laboratory Manual according to laboratories SOPs.

A subset of participants will be regularly tested for SARS-CoV-2 infection. All samples positive for SARS-CoV2 infection will be sequenced to identify escape variants.

DNA analysis of genetic polymorphisms potentially relevant to vaccine immunogenicity and/or SARS-CoV-2 pathogenesis or SARS-CoV-2 therapeutics and gene expression studies amongst others may be performed at the discretion of the Investigators.

This is not an all-inclusive list: additional assays will be performed as more information becomes available about the immune response elicited during the trial.

Should a participant have a SARS-CoV-2 infection, severity should be assessed using the WHO Clinical Progression Scale (see Appendix 2).

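### Infection rates are compared between groups without separating the routinely tested subset, so cohort rate ratios can partly reflect testing intensity

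*Protocol*

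**What the plan says.** Section 5, Table 1 gives four sources for the secondary objective on incidence of infection:

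- self-report: "Self-reported throughout the study duration and assessed at follow up visits";
- scheduled testing of some participants: "Lateral flow testing for SARS-CoV-2 infection in a subset of asymptomatic participants on days 0, 28, 56, 112 and 180", with a nasal PCR swab only after a positive result;
- testing on symptoms: "Ad-hoc PCR testing in all symptomatic patients";
- anti-NP IgG titres, with no limit to a subset.

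Section 12.1 repeats the restriction: "A subset of participants will be regularly tested for SARS-CoV-2 infection". Sections 12 and 13.1 and the footnote to Table 6 agree. The current text does not say who is in the subset. The entry for amendment 3 in section 1 locates it: "Lateral flow tests for all routine asymptomatic SARS-CoV-2 tests for subset of participants at Oxford". Synopsis secondary outcome b describes the scheduled testing without mentioning a subset.

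Section 15.7 includes all enrolled participants in analyses. Section 16.1.3 opens with "Incidence of SARS-CoV-2 infection will be a descriptive analysis" and continues: "Comparison of incidence rates between groups will be performed using Poisson regression". Results are to be given as rate ratios, risk differences, 95% confidence intervals and p values. The section does not say which sources make a case, what the groups are, or how the routinely tested subset is handled.

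**The concern.** A participant in the subset has four extra chances after baseline to have a symptom-free infection found. A participant outside it has none of these. If both kinds of participant enter one rate, the rate depends on the mix as well as on the risk.

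This matters when the groups compared have different mixes. The disease cohorts are not randomised, the subset appears to sit at one site, and no section requires it to be spread evenly. Recruitment to sub-cohorts may also be paused (section 9.3), and cohorts may be expanded or closed (section 6). A cohort ratio with a p value could then be read as a difference in protection when part of it is a difference in testing.

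**Working it through.** **No planned figure to reproduce.** Section 15.3 sizes the trial on IgG (70 per group, 280 in all, 280/0.8 = 350). The protocol gives no infection rate, event count or power.

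**Inputs from the protocol.** Four scheduled tests after baseline (days 28, 56, 112, 180) over 180 days of follow-up.

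**Inputs assumed, because the protocol does not give them.**
- a, the share of infections that are asymptomatic: 20% to 60%
- w, the days a lateral flow test stays positive: 5 to 10
- f, the share of a cohort in the routinely tested subset: several splits
- symptomatic infections are found equally well in everyone, and true incidence is equal in the two cohorts

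**Step 1. Detection by routine testing.** An asymptomatic infection is found if a visit falls within its positive window, so d = 4w/180. This gives 20/180 = 11% (w = 5), 28/180 = 16% (w = 7) and 40/180 = 22% (w = 10).

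**Step 2. Detected rate with routine testing relative to without.** k = [(1 − a) + a·d]/(1 − a) = 1 + d·a/(1 − a).
- Lowest: 1 + 0.111 × 0.25 = 1.028
- Highest: 1 + 0.222 × 1.5 = 1.333

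**Step 3. Apparent rate ratio when the true ratio is 1.** [1 + f1(k − 1)]/[1 + f0(k − 1)].

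| a, w | k | equal shares | 50% v 20% | 70% v 10% | 100% v 0% |
|---|---|---|---|---|---|
| 20%, 5 d | 1.028 | 1.00 | 1.008 | 1.017 | 1.028 |
| 40%, 7 d | 1.104 | 1.00 | 1.030 | 1.062 | 1.104 |
| 60%, 10 d | 1.333 | 1.00 | 1.094 | 1.194 | 1.333 |

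The largest 70% v 10% entry is (1 + 0.7 × 0.333)/(1 + 0.1 × 0.333) = 1.233/1.033 = 1.19.

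**Step 4. If anti-NP conversion also counts as a case in everyone.** Let serology find a share q of asymptomatic infections, equal in all cohorts. The detected rate is then proportional to (1 − a) + a[f(1 − (1 − d)(1 − q)) + (1 − f)q]. For 70% v 10%:
- q = 40%: ratio 1.03 (a = 40%, w = 7) to 1.07 (a = 60%, w = 10)
- q = 80%: ratio 1.01 to 1.02 for the same two settings

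**Step 5. Vaccine arms.** Allocation is randomised 1:1 (section 15.1), so the subset share is equal in expectation and the expected ratio is 1.00.

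**The case against.** The strongest reply is that section 16.1.3 is silent rather than wrong. It does not say that all sources are pooled, and a case definition and model terms often belong in the SAP, which section 16 promises and which is not shown here. Section 15.7 settles who is analysed, not which detections count. This stands in part: the SAP may already solve the problem. But 16.1.3 does fix a between-group model with p values. Unlike 16.1.4 and 16.1.5, it does not defer its details to the SAP. Followed as written, it allows the artefact.

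Several stronger readings are tempting and are not supported:

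- *Everyone outside the subset is tested only when symptomatic.* Self-report and anti-NP IgG are listed for the same objective and are not limited to the subset.
- *The subset is routinely swabbed.* The routine test is lateral flow; the PCR swab follows only a positive result.
- *The cohort ratios are biased.* That needs an uneven spread of the subset, or detection that differs by cohort, and the protocol shows neither. For the translational-blood subset at Oxford, section 6 speaks of choosing patients from each cohort, but whether that is the same subset is not stated.
- *The distortion is large.* A ratio of 1.50 at 100% v 0% would follow if half of infections were asymptomatic and routine testing found half of those. With four tests in 180 days, that needs a mean positive window of 0.5 × 180/4 = 22.5 days; even 30% detection needs 13.5 days. The protocol supports neither.

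The meaning of *groups* is also open. Cohorts are the natural reading, since sections 6, 15.3 and 16.1.2 call the four cohorts groups and 16.1.2 refers to the randomised comparison by vaccine. If vaccine arms were meant, the problem disappears in expectation.

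Finally, sampling error would usually be larger than the artefact. With an assumed 20 events per cohort, the 95% interval spans a factor of exp(1.96 × √(2/20)) = 1.86 either way.

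**Conclusion.** The point holds in a limited form. Ascertainment differs by design between a subset and the rest, and 16.1.3 compares rates between groups with no restriction or stratum for this. Rate ratios between non-randomised cohorts can therefore partly reflect testing intensity, provided that the subset is unevenly spread.

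Under the assumptions above, the artefact is about 1.02 to 1.19 for shares of 70% v 10% and at most 1.33 for 100% v 0%. It is smaller if anti-NP counts as a case and absent if the shares and detection are equal.

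Severity is minor. The endpoint is secondary and introduced as descriptive, no decision rule in the protocol depends on it, and the randomised vaccine comparison is unaffected in expectation.

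**What to change.** In section 16.1.3, and in matching words in the SAP:

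1. State what the groups are and which detection sources make a case.
2. Base the comparison between cohorts on ascertainment common to all: symptomatic or self-reported confirmed infection. An infection found only by a scheduled lateral flow test in someone without symptoms would not count here.
3. Keep anti-N seroconversion as the separate secondary outcome that it already is. Note that it may itself differ by cohort: section 4.1 cites seroconversion after infection of 82% in haematological malignancy, 59% after anti-CD20 therapy and 60% after stem cell transplant, lower than in other patients with cancer.
4. Report asymptomatic infections found by lateral flow only within the routinely tested subset, or stratify any pooled model by routine-testing status (yes/no). A table of subset membership by cohort would show whether the imbalance exists.

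The cost is wording; the analysis uses data already collected. The downside is slightly fewer events in the main comparison.
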